4.9. Lifestyle Restrictions

4.9.1. Female Participants

Female participants of childbearing potential who have a negative serum or urine pregnancy test before enrollment must agree to use one of the highly effective forms of contraception described in [Appendix G](#).

4.9.2. Male Participants

A male participant who is sexually active with a woman of childbearing potential and has not had a vasectomy must agree to use contraception described in [Appendix G](#) during the study treatment period.

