- 10) All participants must have a documented hemoglobin ≥ 9 g/dL within 24 hours prior to the first 2 doses of magrolimab/placebo infusion. Participants who do not meet these criteria must be transfused and have their hemoglobin rechecked to meet the minimum hemoglobin threshold prior to administering each of the first 2 doses of magrolimab/placebo. Transfusions are allowed in order to meet hemoglobin eligibility (see Section 7.10.1.1).
- 11) Female participants of childbearing potential must not be nursing or planning to be pregnant and must have a negative urine or serum pregnancy test within 30 days before randomization and within 72 hours before the first administration of study treatment.
- 12) Male participants and female participants of childbearing potential who engage in heterosexual intercourse must agree to use protocol-specified method(s) of contraception as described in Appendix G.
- 13) Willing to consent to mandatory pretreatment and on-treatment bone marrow biopsies (trephines), unless not feasible as determined by the Investigator and discussed with the Sponsor.

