9. ETHICAL CONSIDERATIONS

This study will be conducted in accordance with the protocol and with the International Council for Harmonisation (ICH) Good Clinical Practice (GCP) guidelines, the Declaration of Helsinki, and any applicable local health authority and IRB/IEC requirements.

To the extent applicable, all references to the ICH, GCP, and the like shall be interpreted as also referring to any corresponding requirements of local regulatory agencies, regulations, and laws. If there is any discrepancy between ICH and local requirements, the most stringent standard shall apply.

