Appendix F. Eastern Cooperative Oncology Group Performance Status

Eastern Cooperative Oncology Group Scale of Performance Status

Publication:

Available online:

<http://ecog-acrin.org/resources/ecog-performance-status>

Accessed 18 February 2020

Appendix G. Pregnancy Precautions, Definition for Female of Childbearing Potential, and Contraceptive Requirements

1. Definitions

a. Definition of Childbearing Potential

For the purposes of this study, a female born participant is considered of childbearing potential following the initiation of puberty (Tanner stage 2) until becoming postmenopausal, unless permanently sterile or with medically documented ovarian failure.

Women are considered to be in a postmenopausal state when they are > 54 years of age with cessation of previously occurring menses for > 12 months without an alternative cause. In addition, women of any age with amenorrhea of > 12 months may also be considered postmenopausal if their follicle stimulating hormone (FSH) level is in the postmenopausal range and they are not using hormonal contraception or hormonal replacement therapy.

Permanent sterilization includes hysterectomy, bilateral oophorectomy, or bilateral salpingectomy in a female participant of any age.

b. Definition of Male Fertility

For the purposes of this study, a male born participant is considered fertile after the initiation of puberty, unless permanently sterile by bilateral orchidectomy or medical documentation.

2. Contraception Requirements for Female Participants

a. Study Drug Effects on Pregnancy and Hormonal Contraception

Magrolimab is contraindicated in pregnancy as a malformative effect has been demonstrated/suspected or is unknown taking into consideration class effect and/or strong suspicion of human teratogenicity/fetotoxicity in early pregnancy based on nonclinical data. For magrolimab, there is no anticipated PK interaction with progestin or other steroids based on the distinct clearance pathways.

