 - Contraceptive vaginal ring

- Barrier methods (each method must be used with a hormonal method)
 - Male condom (with or without spermicide)
 - Female condom (with or without spermicide)
 - Diaphragm with spermicide
 - Cervical cap with spermicide
 - Sponge with spermicide

Inclusion of methods of contraception in this list of permitted methods does not imply that the method is approved in any country or region. Methods should only be used if locally approved.

Female participants must also refrain from egg donation, cryopreservation of cells, and in vitro fertilization during treatment and until the end of contraception requirement. If needed, female participants should be advised to seek advice about egg donation and cryopreservation prior to treatment.

3. Contraception Requirements for Male Participants

Male participants with female partners of childbearing potential must use condoms during treatment and until 3 months after the last dose of azacitidine or magrolimab/placebo, whichever is later. If the female partner of childbearing potential is not pregnant, use of any locally approved contraceptive method should also be considered.

Male participants must also refrain from sperm donation and cryopreservation of cells during treatment and until the end of contraception requirement. If needed, male participants should be advised to seek advice about sperm donation and cryopreservation prior to treatment.

4. Unacceptable Birth Control Methods

Birth control methods that are unacceptable include periodic abstinence (e.g., calendar, ovulation, symptothermal, and postovulation methods), withdrawal (coitus interruptus), spermicides only, and lactational amenorrhea method (LAM). A female condom and a male condom should not be used together.

5. Procedures to be Followed in the Event of Pregnancy

Participants will be instructed to notify the Investigator immediately if they become pregnant at any time during the study or if they become pregnant within 6 months of last study drug dose. Participants who become pregnant or who suspect that they are pregnant during the study must report the information to the Investigator and discontinue study drug immediately. Participants whose partner has become pregnant or suspects she is pregnant during the study must report the information to the Investigator. Instructions for reporting pregnancy and pregnancy outcome are outlined in Section [7.8.2.3](#).

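### Protocol Section 4.9.2 gives men a shorter contraception period, and a looser vasectomy exemption, than Appendix G, which criterion 12 makes the governing rule

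*Protocol*

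**What the plan says.** Four parts of the protocol bear on male contraception.

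- **Section 4.9.2 (Male Participants)** covers a sexually active man whose partner could become pregnant and who "has not had a vasectomy must agree to use contraception described in" Appendix G. It sets the duration as "during the study treatment period".
- **Section 4.7, criterion 12** says that men, and women of childbearing potential, who have heterosexual intercourse "must agree to use protocol-specified method(s) of contraception as described in Appendix G". It gives no end date and no vasectomy exemption.
- **Appendix G, item 3** says that a man whose female partner could become pregnant "must use condoms during treatment and until 3 months after the last dose of azacitidine or magrolimab/placebo, whichever is later". It names no vasectomy exemption.
- **Appendix G, item 1b** treats a man as fertile after puberty "unless permanently sterile by bilateral orchidectomy or medical documentation". Vasectomy is not named.

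**The concern.** Two operative parts of one protocol give different end dates for the same obligation, and the shorter one stands in the section headed for male participants. Appendix G item 2a describes magrolimab as contraindicated in pregnancy and says that azacitidine may harm a fetus. The 3-month tail is the sponsor's own safeguard for partners of treated men. A site that took its duration from 4.9.2 would drop that tail.

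The end date takes effect at each man's last dose, not at enrollment, so the mismatch matters for as long as any man is on treatment or within 3 months of stopping. The vasectomy clause raises a second, smaller question: whether a man whose vasectomy was never confirmed is exempt.

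**Working it through.** There is no design figure to reproduce. The check is a comparison of texts, with one conversion for size.

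**Side by side**

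| Item | Section 4.9.2 | Criterion 12 | Appendix G |
|---|---|---|---|
| End of male contraception | end of the study treatment period | none stated; defers to Appendix G | 3 months after the later of the two last doses (item 3) |
| Vasectomy | any vasectomy exempts | not mentioned | not mentioned in item 3; item 1b requires permanent sterility by orchidectomy or medical documentation |

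**Can the durations be read as the same?**

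1. The treatment period cannot reasonably be stretched to cover follow-up. Section 4.3 lists screening, the treatment period and posttreatment separately, each with its own schedule.
2. The pointer to Appendix G in 4.9.2 does not remove the difference. It takes the method from the appendix and then adds a duration of its own.
3. No rule of precedence settles it. The closest text, in Section 9, reads "If there is any discrepancy between ICH and local requirements, the most stringent standard shall apply". That concerns ICH against local requirements, not one protocol section against another.
4. The matching section for women shows how 4.9.2 could have been written. Section 4.9.1 says that women "must agree to use one of the highly effective forms of contraception described in" Appendix G and sets no end date, so the appendix's end date applies without conflict.

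**Size per affected man**

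- Inputs: 3 months (Appendix G item 3); 30.4375 days per month (the conversion used in SAP Section 5.3); 28-day cycles (Protocol Section 4.3).
- 3 × 30.4375 = 91.3 days.
- 91.3 / 28 = 3.3 cycles.

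**Vasectomy**

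Section 4.9.2 sets no condition that the operation be confirmed. Item 1b would probably cover a confirmed vasectomy through its reference to medical documentation, which leaves the unconfirmed vasectomy as the gap. Elsewhere the appendix applies the stricter standard: item 2b accepts a partner's vasectomy as a method for a female participant only after surgical success has been medically assessed.

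**The case against.** The strongest reply is that the route to harm is narrow. Section 4.9.2 names no method, so a site must open Appendix G to learn what to require, and there the condom rule and the 3-month period stand in one sentence. Criterion 12 has already sent every such man to the appendix at entry. Section 4.9.2 does not say that contraception may stop after treatment, so a site that follows Appendix G satisfies both texts. All of this stands, and it makes an actual early stop less likely. It does not remove the fault: a stated duration is naturally read as the duration, and the one stated is shorter than the sponsor's own rule.

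A reader might infer three stronger things that the documents do not support.

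- **That the ban on sperm donation would also lapse early.** Men must "refrain from sperm donation and cryopreservation of cells during treatment and until the end of contraception requirement", but that ban appears only in Appendix G item 3, directly after the 3-month sentence. Section 4.9.2 does not mention it. A site that knows of the ban has read the longer period.
- **That men with a vasectomy are wrongly exempted as a group.** A documented vasectomy may already fall under item 1b.
- **That men were in fact told to stop early.** The consent form is not among the documents reviewed, so what participants were told is unknown.

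**Conclusion.** The mismatch is real and lies in current text. Section 4.9.2 states a male contraception period 3 months (about 91 days) shorter than the rule that criterion 12 invokes, and nothing in the protocol says which prevails. It also exempts an unconfirmed vasectomy that Appendix G item 1b does not clearly exempt.

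The conclusion assumes that a site could take the duration in 4.9.2 at face value; a site working from criterion 12 and Appendix G is already doing the right thing. How many men are affected cannot be estimated, because the documents give no planned sex split, no partner status and no indication of how sites resolve the two texts. This is a point of participant safety and internal consistency. It has no bearing on endpoints, error control or power. It is worth correcting because the error runs in the unsafe direction and the remedy is small.

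**What to change.** 1. In Section 4.9.2, replace "during the study treatment period" with the Appendix G duration: during treatment and for 3 months after the last dose of azacitidine or of magrolimab/placebo, taking the later of the two.
2. In the same sentence, replace the vasectomy exemption with one for men who are permanently sterile as defined in Appendix G item 1b, and state that this includes a medically documented successful vasectomy. Simply deleting the exemption would not do. Item 3 is not expressly limited to fertile men, so deletion would leave the position of men with a confirmed vasectomy unclear.
3. Notify sites that have men on treatment or within 3 months of their last dose.

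The cost is a small edit to one sentence, the usual submission to ethics committees under Section 9.3 (about 200 sites are planned), and a site notice. Some men would use condoms for up to 3 months longer, and a man with an unconfirmed vasectomy would need documentation or condoms.

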5. STUDY CONDUCT

It is anticipated that this study will take up to 6 years to complete, assuming 22 months for enrollment, plus 1 month screening, 6 or more cycles of study treatment, 30 day and 70 day (or until administration of novel anticancer therapy, whichever is earlier) safety follow-ups for each participant, and up to 4 years of follow-up after the last participant is randomized.

During the study, study assessments will be performed as listed by study visit in Section 4.3 and described in the current section.

5.1. Study Procedures

5.1.1. Pregnancy Test

Pregnancy tests are required only for female participants of childbearing potential. Note that a woman is considered to be of childbearing potential, ie, fertile, following menarche and until becoming postmenopausal (defined as no menses for 12 months without an alternative medical cause) unless permanently sterile. Permanent sterilization methods include hysterectomy, bilateral salpingectomy, and bilateral oophorectomy. A high follicle-stimulating hormone (FSH) level in the postmenopausal range may be used to confirm a postmenopausal state in women not using hormonal contraception or hormonal replacement therapy. However, in the absence of 12 months of amenorrhea, a single follicle-stimulating hormone measurement is insufficient. A urine or serum pregnancy test is required at Screening and within 72 hours before study treatment administration on Cycle 1 Day 1. The Cycle 1 Day 1 pregnancy test does not need to be repeated if the Screening pregnancy test was performed within the 72 hours before study treatment administration. Pregnancy tests will also be required monthly and posttreatment until the end of the contraception requirement.

5.1.2. Complete Blood Counts

Samples for complete blood counts (CBCs) should be collected per the schedules of assessments in Section 4.3. WBC count needs to be $\leq 20 \times 10^3/\mu\text{L}$ prior to randomization and prior to each magrolimab/placebo dose for the first 28 days of magrolimab/placebo dosing and Repriming Cycle (see Section 4.7, Inclusion Criterion 2), for details). Additional samples for CBC may be collected outside of the protocol-specified time points to ensure WBC level $\leq 20 \times 10^3/\mu\text{L}$ for the first cycle and Repriming Cycle.

All participants must have a documented hemoglobin ≥ 9 g/dL within 24 hours prior to the first 2 doses of magrolimab/placebo infusion. Participants who do not meet these criteria must be transfused and have their hemoglobin rechecked to meet the minimum hemoglobin threshold prior to administering each of the first 2 doses of magrolimab/placebo.

5.1.3. Peripheral Blood Smear Assessment

Peripheral smears should be collected per the schedules of assessments and assessed for standard cell morphology. These samples should be collected from the arm contralateral to the arm being used for drug infusion/injection, if possible. All other observed findings should be reported according to local laboratory hematopathology standard procedures. Peripheral smears will be assessed locally (see also Section 7.10.1.3).

5.1.4. Type and Screen and Direct Antiglobulin Test

Magrolimab may interfere with RBC phenotyping due to expected coating of the RBC membrane. Due to the risk of developing anemia, and because magrolimab may make phenotyping difficult, ABO/Rh type, antibody screen, blood phenotyping or genotyping, and DAT need to be performed at screening before exposure to magrolimab, as described in Section 7.10.1.1.

Red blood cell genotyping (instead of an extended RBC phenotyping) must be performed if a participant received any RBC or whole blood transfusion within the previous 3 months (unless the laboratory has availability for special techniques for performing phenotyping for participants with a recent transfusion). RBC genotyping instead of extended RBC phenotyping is acceptable for any participant. Red blood cell phenotyping/genotyping, ABO type, and DAT need not be repeated if results dated before screening are available. Antibody screen need not be repeated if results dated before screening are available, unless the participant was transfused since that time. Results must be available before the first dose of magrolimab.

5.1.5. Vital Signs

Vital signs should include heart rate, respiratory rate, oxygen saturation, blood pressure, temperature, and weight. Height should be recorded during Screening only. Weight should be recorded during Screening and on Day 1 of each cycle. Vital signs are to be recorded prior to infusion/injection of each study treatment at the visits specified in the schedules of assessments in Section 4.3.

5.1.6. Physical Examination

Complete physical examination should be performed at Screening. Thereafter, symptom-directed physical examinations are acceptable and may also include routine examination of the skin (including fingers, toes, and ears) and neurologic system. Symptom-related physical examination should be completed on Day 1 of each cycle or as clinically indicated.

5.1.7. Electrocardiogram

A single electrocardiogram (ECG) will be performed at Screening.

5.1.8. Bone Marrow Assessments

Bone marrow assessments (including aspirate and core/trephine biopsy) are required for response assessments (refer to Section 5.3 and Appendix B), including conventional cytogenetic analysis per institutional standards. In addition, bone marrow specimens may be used for biomarker studies, MRD monitoring, CCI, and biobanking. Minimal residual disease testing will be performed by a central laboratory. Bone marrow aspirate slides for response assessment will also be sent to a central laboratory. Details for preparation and distribution of aspirate and biopsy/trephine specimens to the testing laboratories will be provided in the Laboratory Manual for this study.

Bone marrow assessments include collection of both aspirate and core biopsy (trephine) specimens at each time point according to the schedules of assessments in Section 4.3.

Bone marrow biopsies for response assessments may be adjusted by ± 1 week for Cycle 3 Day 1. After Cycle 3 Day 1, the window is ± 14 days.

Response assessment at End-of-Treatment (EOT) Visit is not required if performed within the last 30 days or progressive disease has been documented. Bone marrow response assessments should continue during long-term follow-up approximately every 8 weeks until transformation to AML is documented or start of new anticancer therapy, whichever comes first. For participants who come off the study treatment to receive an SCT, follow-up for response assessment and collection of SOC bone marrow biopsy/aspirate results will continue until documented relapse or progressive disease occurs. After documented relapse or progressive disease, follow-up for response assessment and collection of SOC bone marrow biopsy/aspirate results will continue until transformation to AML occurs or start of new anticancer therapy, whichever comes first.

5.1.9. Patient-reported Outcomes

Four patient-reported outcome (PRO) instruments will be administered in this study: the Functional Assessment of Cancer Therapy-Anemia (FACT-Anemia), the 5-level EuroQol 5 dimensions (EQ-5D-5L), the Patient Global Impression of Severity (PGIS), and the Patient Global Impression of Change (PGIC). The participant should complete these questionnaires before any other study procedures at required visits.

5.1.9.1. FACT-Anemia

The FACT-Anemia questionnaire is a 47-item instrument used to assess anemia- and fatigue-related quality of life for patients with cancer and chronic disease. A sample is provided in Appendix C. This instrument consists of 5 subscales, including physical well-being, emotional well-being, functional well-being, social well-being, and anemia symptoms. Each subscale measures items on a 5-point Likert scale from 0 to 4, where 0 = not at all and 4 = very much. The FACT-Anemia instrument has demonstrated good validity and reliability in the general population as well as in patients with cancer {Cella 2012, Revicki 2013}.

5.1.9.2. EQ-5D-5L

The EQ-5D-5L is an instrument for use as a measure of health outcome {[EuroQol Research Foundation 2017](#), [Janssen 2013](#)}. The EQ-5D-5L consists of 2 sections: the EQ-5D descriptive system and the EuroQol visual analogue scale (EQ VAS). A sample is provided in [Appendix D](#).

The descriptive system comprises 5 dimensions: mobility, self-care, usual activities, pain/discomfort, and anxiety/depression. Each dimension has 5 levels: no problems, slight problems, moderate problems, severe problems, and extreme problems. The participant is asked to indicate his/her health state by ticking the box next to the most appropriate statement in each of the 5 dimensions. This decision results in a 1-digit number that expresses the level selected for that dimension. The digits for the 5 dimensions can be combined into a 5-digit number that describes the participant's health state.

The EQ VAS records the participant's self-rated health on a vertical visual analogue scale, where the endpoints are labeled "The best health you can imagine" and "The worst health you can imagine." The EQ VAS can be used as a quantitative measure of health outcome that reflects the participant's own judgment.

5.1.9.3. PGIS/PGIC

The PGIS and PGIC assessments are both single-item assessments used to demonstrate sensitivity and meaningful change thresholds and bolster the validity of selected PRO assessments {[Department for Health and Human Services \(DHHS\) 2018](#)}. A sample of these questionnaires is provided in [Appendix E](#).

5.1.10. Adverse Events

At each visit, the following AEs are to be reported using the applicable electronic case report form (eCRF; Section [10.2.3.1](#)):

- After informed consent, but prior to initiation of study treatment, all AEs related to protocol-mandated procedures.
- After the first dose of study treatment, all AEs observed by the Investigator or reported by the participant that occur through 30 days after last dose of study treatment. Adverse events occurring after 30 days of last dose of study treatment will be reported until either 70 days after the last dose or until the initiation of new anticancer therapy (including SCT), whichever is earlier.

Details of adverse event reporting can be found in Section [7.2](#).

